Continuous Glucose Monitoring in Patients with End-Stage Kidney Disease and Burnt-Out Diabetes

1. Study Summary

| | |
|---|---|
| Project Title | Continuous Glucose Monitoring in Patients with End-Stage Kidney Disease and Burnt-Out Diabetes |
| Project Design | Observational cross-sectional study. |
| Primary Objective | 
To determine if utilizing Continuous Glucose Monitor (CGM) devices is superior to HbA1c for assessing glycemic control in patients with end-stage kidney disease on dialysis. |
| Secondary Objective(s) | 
Compare daily mean glucose values between patients with burnt-out diabetes and non-diabetic subjects with ESKD. |
| Research Intervention(s)/Interactions | 
Continuous glucose monitoring (CGM) compared to glycemic metrics including CGM and HbA1c. |
| Study Population | Individual with and without diabetes on hemodialysis and with HbA1c < 6.5% on no diabetes therapy will be eligible to enroll. |
| Sample Size | 40 patients. 20 patients with burnt-out diabetes and 20 non-diabetic subjects with ESKD |
| Study Duration for individual participants | 10 days |
| Study Specific Abbreviations/ Definitions | POC, Bedside point-of-care; CGM, Continuous glucose monitoring; T2D, Type 2 diabetes; BG, blood glucose; OAD, Oral antidiabetic; MARD, mean absolute relative difference; CBG, capillary blood glucose |
| Funding Source (if any) | N/A |

2. Objectives

Diabetes is the number one cause of end stage kidney disease (ESKD) and need for dialysis. It is estimated that diabetes affects up to 40% of patients with ESKD³. Glycosylated hemoglobin (HbA1c) is the gold standard to assess glycemic control in patients with diabetes and indicates the average glycemia during the past 2-3 months. In subjects with ESKD; however, the accuracy of HbA1c is reduced because of anemia, shortened erythrocyte lifespan, erythropoietin therapy, among others factors. To overcome the limitations of HbA1c, continuous glucose monitoring (CGM) technology has been shown to provide a comprehensive glycemic control in patients with diabetes and may overcome the limitations of these methods in the ESKD population; however, the accuracy of CGM in ESKD has not been established.

About one fourth of patients with diabetes on dialysis therapy experience resolution of their hyperglycemia, as defined by an HbA1c less than 6.5%, without antidiabetic therapy. This

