[name], Professor of Statistics at the School of Public Health will assist with data analysis. We will measure outcomes such as average daily glucose, time in range between 70-140 mg/dL, time in range between 70-180 mg/dL, fasting, premeal, 2 hours post meal, and nocturnal (10 PM-6:00 AM) glucose values, time (%) in hyperglycemia (>180 mg/dL, >250 mg/dL). In addition, we will collect information on glycemic variability by CGM.

Sample Size. This study will be a pilot study, as there is no preliminary data available for this patient population utilizing the Dexcom G6 CGM. Currently, there are 850 patients undergoing Hemodialysis at Emory Dialysis Centers. Up to 40% of these cases should be due to diabetes mellitus, and anywhere from \sim 25-35% of these patients should meet the definition of burnt-out diabetes, resulting in \sim 100 patients who should qualify as participants. Currently, we have identified \sim 20 patients with burnt-out diabetes on hemodialysis.

8. Data and/or Specimen Banking

Data collection records with personal identifiers will be stored in locked file cabinets. Presentation of the study results at regional or scientific meetings or in publications will not identify subjects. Access to research and confidential records will be limited to clinical investigators, research coordinators, and the IRB at Emory University.

9. Sharing of Results with Participants

Study results will be shared with the subjects at their request, including laboratory values, blood pressure measurements, and physical exam measurements.

10. Study Timelines

All consenting subjects, with and without diabetes, will have a Dexcom G6 CGM placed for up to 10 days (study duration). The CGM sensor will be removed after 10 days.

The anticipated time required to complete primary analysis of results is 6 -9 months

11. Inclusion and Exclusion Criteria

Inclusion Criteria

1. Be at least 18 years old
2. Dialysis treatment for more than 3 months
3. HbA1c less than 6.5% at the first clinic visit
4. Willing to wear a CGM for 10 days

Exclusion criteria

1. Have used insulin or any diabetes treatment during the last 3 months
2. Be pregnant or plan to become pregnant during the study
3. Known allergy to medical-grade adhesives

4. Taking acetaminophen (more than 1 gram every six hours) or hydroxyurea (may interfere with sensor membrane)
5. Current or anticipated use of stress steroid doses (prednisone \leq 5 mg or its equivalent is allowed)

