Most participants will not be of child-bearing age. However, pregnancy may impact the accuracy of the CGM device. We will ask all women of their menopausal status. If a woman is of child-bearing age, we will administer a pregnancy test before enrolling in the trial.

12. Population

This study will be a pilot study, as there is no preliminary data available for this patient population utilizing the Dexcom G6 CGM. Patients qualify for the burnt-out diabetes group if they have 1. Been diagnosed with diabetes in the past, 2. Now have last A1c of $<6.5\%$, and 3. Are no longer on any diabetic medications, and meet all other inclusion and exclusion criteria. Patients may qualify for the control group if they have never been diagnosed with diabetes in the past and meet all other inclusion and exclusion criteria.

Currently, there are 850 patients undergoing HD. ~40% of these cases should be due to diabetes mellitus, and anywhere from ~25-35% of these patients should meet the definition of burnt-out diabetes, resulting in ~100 patients who should qualify as participants. Currently, we have identified ~20 patients with burnt-out diabetes on hemodialysis.

13. Vulnerable Populations

This study does not involve a vulnerable population.

14. Local Number of Participants

A total of 40 subjects will be invited to participate from Emory dialysis centers.

15. Recruitment Methods

Recruitment will involve identification of hospitalized patients at Emory dialysis centers who meet the study eligibility criteria. Screening for eligibility will be performed from medical records prior to informed consent being signed. There will be no specific efforts to promote recruitment other than making hospital staff aware of the study. All eligible participants will be included without regard to sex, race, or ethnicity. Participation in this study is voluntary.

Recruitment: The study team will perform pre-screening on subjects scheduled for their clinic visit and will approach potential candidates during the dialysis session. If potential candidate expresses interest and qualifies for study participation, full consent procedure will be conducted during/after their hemodialysis sessions. All consenting subjects, with and without diabetes, will have a Dexcom G6 CGM placed for up to 10 days (study duration).

16. Withdrawal of Participants

1. The subject may withdraw at will at any time.

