To assure each subject's confidentiality, data collected under this protocol will be coded and stored in a secure locked file cabinet with access limited to those directly related to the conduct of this study. Electronic versions of these data will be stored on a limited access, password protected, secure server with coded patient identifiers. Study participants will be assigned a code number that will be linked to their name. Only study personnel will have access to the linked name-code key. Except for the informed consent form, data will be marked solely with the participant's code number.

Statistical analysis

The primary endpoint in this study is to compare glycemic metrics including CGM and HbA1c in patients with burnt-out diabetes and in non-diabetic subjects with ESKD. We will first compare clinical characteristics including demographics, duration of diabetes and dialysis between patients with and without DR using two-sample t-tests or nonparametric Wilcoxon tests. We will perform multivariate linear regression to evaluate the group difference while accounting other possible confounders (patient age, type of dialysis) for the primary outcome. The secondary endpoints include compare daily mean glucose values between patients with burnt-out diabetes and non-diabetic subjects with ESKD, most recent HbA1c, comorbidities (hypertension, cardiovascular disease, heart failure, peripheral neuropathy, autonomic/GI neuropathy, cerebrovascular disease, peripheral vascular disease, depression, anxiety, cognitive impairment/dementia), adherence and barriers to screening recommendations, we will analyze continuous secondary outcomes in the same way that we propose for the primary endpoint. A p-value less than 0.05 will be considered significant. The data will be presented as means \pm SD. Statistical analysis will be performed using the SAS (version 9.2; SAS Institute, Cary, NC).

Confidentiality

All data and records generated during this study will be kept confidential in accordance with Institutional policies and HIPAA on subject privacy. The Principal investigator and other study personnel will not use data or PHI for any purpose other than conduction of the study. All PHI used will be de-identified and coded by the Principal investigator or designee. The code will be kept in a password protected computer file. PHI will be disclosed when required for audit by regulatory agency.

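### Both groups must have HbA1c below 6.5% to enter, so the planned comparison cannot support a conclusion that CGM is superior to HbA1c

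*Combined protocol and SAP*

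**What the plan says.** **Objective.** Section 1 gives the primary objective as "To determine if utilizing Continuous Glucose Monitor (CGM) devices is superior to HbA1c for assessing glycemic control in patients with end-stage kidney disease on dialysis". Hypothesis 1 (Section 2, Specific Aims) makes the same claim. It adds that the burnt-out group will have higher mean daily glucose and more time above 180 mg/dl.

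**Entry.** Section 1 describes the population as "Individual with and without diabetes on hemodialysis and with HbA1c < 6.5% on no diabetes therapy will be eligible to enroll". Section 11 requires, of everyone, "HbA1c less than 6.5% at the first clinic visit". Section 12 defines the burnt-out group as having "Been diagnosed with diabetes in the past, 2. Now have last A1c of" below 6.5% and no longer taking diabetes medication. Controls are those who have "never been diagnosed with diabetes in the past and meet all other inclusion and exclusion criteria", so the HbA1c limit applies to them too.

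**Analysis.** Under Section 6, HbA1c is taken from the medical record. Section 20 states "The primary endpoint in this study is to compare glycemic metrics including CGM and HbA1c in patients with burnt-out diabetes" and in non-diabetic ESKD controls, analysed by linear regression of the group difference. It lists "most recent HbA1c" again among the secondary endpoints. Section 4, in contrast, names only CGM quantities as primary: hypoglycaemia frequency and mean daily glucose.

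**The concern.** HbA1c is used to select both groups and is then one of the two measures compared between them. Selecting on a marker shortens its range, which shrinks its group difference and its correlation with true glycaemia. A marker not used for selection loses less. If CGM then shows a group difference and HbA1c shows little, readers will tend to take this as support for Hypothesis 1, although selection alone pushes the data that way. At stake is the headline claim of the study, not the CGM data themselves.

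**Working it through.** The plan gives 40 participants (20 per group) as a pilot, with no power, effect size or SD, so there is no calculation to reproduce.

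**1. Detecting hyperglycaemia (no assumptions).** If the analysed HbA1c is the eligibility value, every participant is below 6.5%, so HbA1c flags 0 of 40 whatever the truth. CGM is not truncated and can flag any number. Because no reference is defined, a false CGM alarm could not be recognised as one. A record HbA1c other than the eligibility value would escape the truncation only partly.

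**2. Standardised group differences (illustration).** Assumptions not in the documents:
- True glycaemia has SD 1 within each group and is shifted by m = 1-2 SD in diabetes.
- HbA1c and CGM each equal truth plus independent normal error, with the same reliability r = 0.5-0.7.
- The HbA1c cut-off is passed by p = 25-35% of diabetic patients, borrowing the share in Sections 7 and 12.

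Before selection, both markers have d = m√r, from 1 × √0.5 = 0.71 to 2 × √0.7 = 1.67.

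Worked example with m = 1.5, r = 0.5, p = 25%:
- Before selection, d = 1.5 × √0.5 = 1.06 for both markers.
- Marker SD is √(1/0.5) = 1.414. The cut-off is 1.5 - 0.674 × 1.414 = 0.55.
- HbA1c after selection (truncated normal): means -0.298 and -0.805, variances 0.483 and 0.912. So d = 0.508 / √0.697 = 0.61.
- CGM after selection: means 1.5 + 0.5 × (-0.298 - 1.5) = 0.601 and 0.5 × (-0.805) = -0.403. Variances are 0.5 + 0.25 × 0.483 + 1 = 1.621 and 0.5 + 0.25 × 0.912 + 1 = 1.728. So d = 1.004 / √1.674 = 0.78.
- Power at 20 per group, two-sided 0.05, is about 47% for HbA1c and 67% for CGM.

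Simulation over the 12 combinations (m = 1, 1.5, 2; r = 0.5, 0.7; p = 25%, 35%) gave:

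| | HbA1c | CGM |
|---|---|---|
| d before selection | 0.71-1.67 | 0.71-1.67 |
| d after selection | 0.38-1.14 | 0.51-1.23 |
| Correlation with truth after selection | 0.52-0.81 | 0.66-0.84 |

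CGM was ahead in all 12, by about 0.06-0.21 SD.

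**3. How far this depends on the cut-off.** The same cut-off excludes a share 1 - Φ(z_p + m√r) of controls:
- Worked example: 1 - Φ(-0.674 + 1.061) = 35%.
- Highest (m = 1, r = 0.5, p = 25%): 1 - Φ(0.033) = 49%.
- Lowest (m = 2, r = 0.7, p = 35%): 1 - Φ(1.288) = 10%.

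Nothing in the documents supports excluding that many never-diagnosed patients. The 25-35% is also the share meeting the whole burnt-out definition, including being off medication, and not the share below 6.5%. If instead 97.5% of controls pass, with the same shifts, the gap is about 0.01-0.06 SD and 1-3 points of power. If 95-99% of controls and 25-35% of diabetic patients pass, the shift must be 2.4-4.2 SD. The gap is then about 0.06-0.25 SD, but both markers have at least 99% power.

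**4. How often CGM alone would be significant.** In simulated studies of 20 per group under step 2, CGM was significant and HbA1c not in about 4-31%. In the worked example this happened in 31%, the reverse in 11%, and the two tests agreed in 58%.

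**5. Adjusting for HbA1c.** With equally accurate markers, regressing CGM on group and HbA1c gives a group coefficient of m(1 - r). This runs from 1 × 0.3 = 0.30 to 2 × 0.5 = 1.00 SD of true glycaemia, from HbA1c measurement error alone.

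**The case against.** HbA1c below 6.5% is part of what burnt-out diabetes means, so the restriction cannot be designed away. Section 4's primary endpoints use CGM alone, and the rationale in Sections 2 and 3 is to learn whether these patients are truly normoglycaemic. That question survives: comparing CGM mean glucose and time above range between the groups is sound. Pilot status excuses low power, but not a superiority claim that the design cannot test.

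A reader might infer that the plan will declare CGM the better tool whenever CGM separates the groups and HbA1c does not. The documents state no such rule. Section 20 regresses the group difference and contains no head-to-head test. The superiority objective would therefore lack a test and a reference even without the HbA1c restriction. Sections 2 and 3 say CGM accuracy in ESKD is not established. Glycated albumin and fructosamine are drawn (Section 6), but neither statistical section uses them, and Section 3 notes their own limits.

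A reader might also infer that significance on CGM alone is the expected result when the markers are equally accurate. Step 4 does not support that: it is more likely than the reverse, but still a minority outcome. Nor should the 47% versus 67% contrast be taken as typical, since it rests on excluding 35% of controls.

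**Conclusion.** The point stands as a limit on inference. In detecting hyperglycaemia the advantage to CGM is absolute on the eligibility value and needs no assumptions. On standardised means it is directional and modest: about 0.06-0.21 SD under the 25-35% cut-off and about 0.01-0.06 SD if nearly all controls pass with shifts of 1-2 SD. It is larger when reliability is low. The tilt does not guarantee a CGM win on means: with a 2 SD shift and reliability 0.7 for HbA1c against 0.5 for CGM, HbA1c stayed ahead after selection (1.10 against 0.97). These sizes rest on assumed shifts, reliabilities and cut-offs; only the 0 of 40 follows from the documents alone. It would be wrong to conclude that the study as a whole is invalid.

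**What to change.** 1. In Section 1 and Hypothesis 1, replace the superiority and better-tool claims with the question whether patients with burnt-out diabetes and HbA1c below 6.5% have higher CGM glucose than non-diabetic ESKD patients with HbA1c below 6.5%.
2. In Section 20, keep the between-group CGM comparison as primary. Align its wording with Section 4, because Sections 1 and 20 currently list daily mean glucose as secondary. Report HbA1c descriptively as a selection variable, and state that its between-group test is not evidence on which tool is better.
3. Report the share of each group with CGM hyperglycaemia despite HbA1c below 6.5%, with a 95% CI, using a prespecified per-participant measure based on the protocol's own >180 mg/dl threshold. With 20 per group, a share of 50% has a half-width of about 1.96 × √(0.25/20) = 22 percentage points. Some non-zero share is to be expected in any case, so show the control group beside it.
4. An HbA1c-adjusted CGM group difference may be added as a descriptive secondary analysis, but not as the primary one. It needs the warning that HbA1c measurement error alone makes it positive when the markers are equally accurate (step 5).

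The cost is wording and analysis of data already planned. The price is a narrower claim, limited to patients with HbA1c below 6.5%.

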Continuous Glucose Monitoring in Patients with End-Stage Kidney Disease and Burnt-Out Diabetes

phenomenon is known as “burnt-out diabetes”. Because HbA1c may be falsely low in ESKD, we will use CGM to assess glycemic control and confirm whether patients with burnt-out diabetes have normoglycemia or not. We hypothesize that the use of CGM may represent a better tool to assess glycemic control than HbA1c in patients with ESKD on dialysis. To prove this hypothesis, we will compare glycemic metrics including CGM and HbA1c, in 20 patients with burnt-out diabetes and in 20 non-diabetic subjects with ESKD.

II. Specific Aims:

Study Aim. Compare glycemic metrics including CGM and HbA1c in patients with burnt-out diabetes and in non-diabetic subjects with ESKD.

Hypotheses:

1. The use of CGM represents a better tool to assess glycemic control than traditional markers (HbA1c) in patients with ESKD and renal replacement therapy (dialysis). Patients with burnt-out diabetes will show higher mean daily glucose values and higher time-above range (TAR > 180 mg/dl) compared to non-diabetic subjects with ESKD.

3. Background

Diabetes and chronic kidney disease. More than 37 million adults, or 14.7% of all Americans aged 18 and older, are living with diabetes. Controlling hyperglycemia is foundational to diabetes management and is necessary to reduce the risks of chronic diabetes complications and death. Diabetic nephropathy accounts for great morbidity, as diabetes is the number one cause of chronic kidney disease (CKD) and end stage kidney disease (ESKD) in the US². It is estimated that diabetes affects up to 40% of patients with ESKD³.

Assessment of glucose control in patients with advanced CKD/ESKD is complex due to changes in glucose homeostasis, potential effects on assays of glycemia, and altered pharmacokinetics of diabetes medications². Glycosylated hemoglobin (HbA1c) has been the gold standard to assess glycemic control in patients with diabetes. HbA1c reflects the average glycemic value over approximately 3 months. Although HbA1c is associated with chronic complications of diabetes in patients with normal kidney function, its predictive value is uncertain in patients with increased red cell turnover (hemolysis) and in subjects with ESKD or eGFR <30 ml/min. HbA1c reliability in ESKD is reduced because of anemia, shortened erythrocyte lifespan, protein-energy wasting, and malnutrition-inflammation cachexia syndrome, among others^{4,5}.

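### HbA1c is tested between groups although entry caps it below 6.5% in both, so a smaller HbA1c than CGM difference is expected even if the two markers are equally accurate

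*Combined protocol and SAP*

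**What the plan says.** - **Objective.** Section 1 gives the primary objective as "To determine if utilizing Continuous Glucose Monitor (CGM) devices is superior to HbA1c for assessing glycemic control". Section 2 states the hypothesis that CGM is the better tool and continues: "To prove this hypothesis, we will compare glycemic metrics including CGM and HbA1c", in the two groups of 20.
- **Analysis.** Section 20 sets the primary endpoint as a between-group comparison ("compare glycemic metrics including CGM and HbA1c in patients with burnt-out diabetes and in non-diabetic subjects with ESKD"), analysed by linear regression for the group difference. The secondary list includes HbA1c again ("non-diabetic subjects with ESKD, most recent HbA1c, comorbidities"), with continuous secondary outcomes analysed in the same way. The significance level is 0.05.
- **Eligibility.** Section 11 requires "HbA1c less than 6.5% at the first clinic visit". Section 1 applies this to people "with and without diabetes on hemodialysis and with HbA1c < 6.5% on no diabetes therapy will be eligible to enroll". Section 12 applies it to controls, who qualify "if they have never been diagnosed with diabetes in the past and meet all other inclusion and exclusion criteria".
- **Source of HbA1c.** Section 6 (Visit 2) takes HbA1c from the medical record. Sections 15 and 25 also screen from records, so the analysed value is probably the one that qualified the patient.
- **Section 4** lists only CGM endpoints (hypoglycemia and mean daily glucose).

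No section mentions the truncation. No section plans a marker-to-marker analysis such as agreement, correlation, or comparison of both markers with a reference.

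**The concern.** The plan selects patients on one of the two markers it then compares. The cap hardly touches controls but removes the upper part of the HbA1c distribution among people with past diabetes. That pulls the group means together on HbA1c. It pulls them together on CGM only as far as CGM follows HbA1c.

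At stake is the headline inference. A clear CGM difference beside a small or non-significant HbA1c difference could be read as HbA1c missing hyperglycemia that CGM detects. Some of that pattern would come from the entry rule whatever the quality of HbA1c, and it lies in the hypothesised direction.

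**Working it through.** **Inputs from the documents.** Cap 6.5% in both groups (Sections 1, 11, 12); 20 per group (Section 1); significance level 0.05 (Sections 7 and 20; sidedness not stated, two-sided assumed). No mean, SD, correlation or effect size is given.

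**The plan's own figure.** Sections 7 and 12 expect about 100 eligible patients: 850 × 0.40 = 340; 340 × 0.25 = 85 and 340 × 0.35 = 119. This reproduces. However, the 25-35% is the share meeting the whole burnt-out definition, which also requires being off diabetes medication. The share that the cap alone removes is not given, so it is varied below.

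**Model (assumptions).** HbA1c is normal with mean m and SD s in each group. CGM, in HbA1c-equivalent units, has the same mean and SD and correlation ρ with HbA1c. With z = (6.5 − m)/s and λ = φ(z)/Φ(z), patients kept under the cap have

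- mean HbA1c = m − sλ
- mean CGM = m − ρsλ

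Let Δ be the unselected gap and k = (sλ in diabetes) − (sλ in controls). Then the HbA1c gap is Δ − k and the CGM gap is Δ − ρk. CGM is ahead by (1 − ρ)k, which is positive whenever ρ < 1 and the cap cuts the diabetes group harder.

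**Central case.**

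- Controls: m = 5.3, s = 0.5, z = 2.4, sλ = 0.011.
- Diabetes: s = 1.0, 30% below 6.5%, so m = 6.5 + 0.524 = 7.024 and sλ = 0.3477/0.30 = 1.159.
- Δ = 7.024 − 5.3 = 1.724; k = 1.159 − 0.011 = 1.148.
- HbA1c gap: 1.724 − 1.148 = 0.58.
- CGM gap, ρ = 0.7: 1.724 − 0.7 × 1.148 = 0.92. At ρ = 0.85: 0.75.
- Re-measured HbA1c correlating 0.9 with the qualifying value: 1.724 − 0.9 × 1.148 = 0.69.

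**Other settings.** ρ = 0.7, control SD 0.5. Gaps come from the formula. Significance rates come from simulated two-sided t-tests, 20 against 20, standing in for the plan's adjusted regression.

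| Diabetes patients below 6.5% | Control mean | Diabetes SD | Unselected gap | HbA1c gap | CGM gap | Only CGM significant | Only HbA1c significant |
|---|---|---|---|---|---|---|---|
| 30% | 5.3 | 0.8 | 1.62 | 0.70 | 0.98 | under 1% | under 1% |
| 30% | 5.3 | 1.0 | 1.72 | 0.58 | 0.92 | 7% | under 1% |
| 30% | 5.6 | 1.0 | 1.42 | 0.31 | 0.64 | 37% | 3% |
| 30% | 5.6 | 1.3 | 1.58 | 0.12 | 0.56 | 46-47% | 1-2% |
| 50% | 5.3 | 0.8 | 1.20 | 0.57 | 0.76 | 5% | 1% |
| 50% | 5.3 | 1.0 | 1.20 | 0.41 | 0.65 | 24% | 5% |
| 70% | 5.3 | 0.8 | 0.78 | 0.39 | 0.51 | 19% | 8% |
| 70% | 5.3 | 1.0 | 0.68 | 0.19 | 0.34 | 19% | 6% |

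In the central case power is 92-93% for HbA1c and 99% for CGM, so the distortion there is mainly in the size of the difference.

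**Second model.** Each marker equals true glycemia plus independent error of the same SD. Assumed: control mean 5.3 or 5.5, SD 0.35; past-diabetes mean 6.3-7.0, SD 0.8-1.0; error SD 0.3-0.7. In all 24 scenarios the cap shrank the HbA1c gap more.

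- Example (5.5 against 6.5, SD 0.35 and 0.8, error SD 0.5): a gap of 1.00 on both markers becomes 0.31 on HbA1c and 0.48 on CGM, with power 0.42 and 0.57. Only CGM is significant in 26% of trials, only HbA1c in 11%. Without the cap each occurs in about 2%.
- With error SD 0.3 the rates are 1-17% and 0-9%; with error SD 0.7, 14-33% and 2-12%.
- A fresh HbA1c restores equality with CGM (power 0.57) only if none of its error persists. If half the error variance persists, power is 0.48.

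**The case against.** **The plan states no rule that a null HbA1c difference counts for CGM.** This is true, and a reader should not infer such a rule. The directional hypothesis concerns CGM values only, and Section 4 lists only CGM endpoints. But Section 2 ties the two-marker group comparison to the better-tool hypothesis, Section 20 tests HbA1c, and no other analysis serves the superiority objective.

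**The cap is legitimate.** It defines burnt-out diabetes, and asking whether such patients are truly normoglycemic on CGM requires patients selected on HbA1c. This stands. The point is confined to HbA1c as a tested outcome and to inference about which marker is better.

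**The size is driven by assumptions.** This also stands. In the central case both tests usually succeed, and the effect is small when marker error is small. A reader might take from the 25-35% that the cap removes 65-75% of patients with diabetes. The documents do not support that, because the percentage also requires being off therapy and so reflects exclusion of treated patients too.

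**An attenuated difference is not an empty one.** Correct: the HbA1c gap does not vanish, and it would be too strong to say that the test carries no information. What it cannot do is show which marker is better.

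**Conclusion.** The concern holds in direction; its size is uncertain. Selection on HbA1c below 6.5% shrinks the HbA1c group difference more than the CGM difference in every setting examined, although the markers were made equally accurate.

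If 30% of patients with diabetes fall below the cap, the gaps are 0.12-0.70 for HbA1c against 0.56-0.98 for CGM. CGM alone is then significant in under 1% to about 47% of trials, against at most about 3% for the reverse. If 50-70% fall below it, the rates are 5-24% against 1-8%. These figures rest on assumed normal distributions, SDs and a correlation of 0.7; a higher correlation narrows the asymmetry.

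The HbA1c group test therefore gives no interpretable evidence on which marker is better. The between-group CGM comparison remains valid for the population enrolled.

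**What to change.** - **Section 20:** remove HbA1c from the tested primary and secondary endpoints, in line with the CGM-only endpoints of Section 4. Report it by group as an entry characteristic, without a p-value.
- **Sections 2 and 20:** state that a small or null HbA1c difference is expected from the entry rule and will not be cited as evidence that CGM is superior to HbA1c.
- **Between-group claim:** limit it to CGM outcomes among untreated dialysis patients with HbA1c below 6.5%.

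The cost is wording and one dropped test; no new data, patients or procedures are needed. The downside is that the superiority objective in Section 1 can no longer rest on the group contrast. As the plan stands, no other analysis supports that objective, so it would need either a within-patient or reference-based comparison of the markers or a narrower statement.
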